- 2. Measurements of endometrial thicknesses in subjects with a uterus at study end, comparing results to baseline measurements.
- 3. Changes in tissue lymphocyte densities and neuronal hyperplasia comparing baseline to study end.
- 4. Levels of dyspareunia measured by the Numerical Rating Scale (NRS) during regimens of nightly estradiol therapy applied to the vulvar vestibule, determining how soon and how uniformly this schedule corrects painful penetration in study subjects.

Secondary endpoints:

- 1. Pain descriptors as measured by the modified Vulvar Pain Assessment Questionnaire—screen (VPAQ-screen) (Dargie, 2016)
- 2. Sexual function evaluated using the validated but modified VPAQ-Screen.
- 3. Sexual distress as measured by the (VPAQ-Screen).
- 4. Lower Urinary Tract symptoms (LUTS) of menopause as measured by a set of validated questions.
- 5. Vestibular tenderness as measured clinically by the cotton swab touch test and the lidocaine test.
- 6. Vaginal and vestibular atrophy as measured by visual examination and pH of the vaginal secretions.
- 7. Characterization of the urogenital microbiome via swabs collected from the vestibule and vagina.

3. Background

Pain with sex is a common problem experienced by women after the age of menopause, and it is commonly termed "vulvovaginal atrophy" or "vaginal dryness" by most clinicians (ACOG, 2008). Genitourinary Syndrome of Menopause (GSM) is the new term put forth by two professional societies (Portman, 2014). Vulvar complaints develop in association with loss of ovarian estrogens, and the prevalence of sexual pain in women over 50 is 50% (ACOG, 2008). Symptoms are chronic and tend to worsen over time (Gass, 2013). The relationship of vulvar symptoms to sexual difficulties is well established (Simon, 2014). However, the research into this problem is variable in its focus, and there are many gaps.

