For mild symptoms, sexual lubricants have proven to be of help. For significant vulvovaginal symptoms, estrogen therapy has been found to be the most effective therapy according to the Cochrane review of 2006 (Suckling, 2006). But even in well-designed studies of symptomatic women, the array of symptom complaints is broad and includes annoying rather than significant symptoms. Studies that include many women with mild complaints like "dryness" or 'itching,' are not fully representative of women with actual intimacy pain. Allodynia is pain from touch that normally would not hurt, and therefore it is an appropriate term with which to characterize dyspareunia.

Nastri, in her 2013 Cochrane review of estrogen and sexual function in menopause, found that no study of estrogen therapy was focused solely on women with sexual dysfunction in postmenopause. Only five of 27 studies evaluated sexual function as a primary outcome among other menopause symptoms. In those women, estrogen had only a "small to moderate" benefit (Nastri, 2013). One multi-country study of 4100 women has documented that 38% of those using estrogen products found them to be inadequate to correct genital pain (Nappi, 2013). Kao found that the mean pain score in postmenopausal women with penetration pain was 7 on a scale of 0-10 (SD 2.5) and 30% of her cohort were using estrogen products (Kao, 2014). General population studies indicate that a significant proportion of older women value their continued sexual activity (Schneidewind-Skibbe 2008).

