 - iv. A history of peak menopausal symptoms >2 year prior in women age>51 with no functioning uterus (previous ablation or hysterectomy)
 - v. FSH >40 in women of age >51 if they have no prior history of classic menopausal symptoms (hot flashes, night sweats) and have 1 ovary but amenorrhea that was surgically induced (by ablation or hysterectomy)
- 3. Onset of dyspareunia after menopause but not before.*
- 4. Stable heterosexual partnership ≥1 years (or by investigator discretion if less than 1 years) and both partners want to have more satisfying penetrative intimacy.
- 5. No estrogen product use, local or systemic, for 6 months.
- 6. More than 6 months of consistent insertional pain with intercourse (may have stopped having intercourse due to this consistent experience of pain).*
- 7. Willingness to enter a study where she will receive low-dose local estrogen.*
- 8. Willingness to enter a study that requires application of cream on a frequent schedule for 3 months. *
- 9. Willingness to evaluate the progress of therapies by use of the Tampon Test as many as 2 times per week, and willingness to attempt intercourse if the Tampon Test indicates tolerable penetrative pain.*

Exclusion Criteria

- 1. Consistently has pain in the pelvis or low abdomen (chronic pelvic pain)
- 2. Negative cotton-swab touch test in the vulvar vestibule* or vestibular tenderness that is not extinguishable by application of lidocaine 4% topical solution applied for 3 minutes.
- 3. Partner with sexual dysfunction limiting his performance or making it inconsistent. (The use of male therapy for erectile dysfunction is acceptable.)
- 4. Diagnosis by a physical therapist or clinician of significant pelvic floor muscle tension causing pain (pelvic floor myalgia) or has been found on screening examination to have pelvic floor tenderness or bladder tenderness.
- 5. Constant burning pain localized to the vulva.
- 6. Allergy to local estrogen products or lidocaine numbing agents.*
- 7. Previous estrogen receptor positive breast cancer or endometrial cancer or has been cautioned about estrogen because of any other cancer
- 8. Endometrial thickness ≥5mm on screening via transvaginal ultrasound.
- 9. Vulvovaginitis assessed at screening exam.

^{*}n/a for reference group

^{*}n/a for reference group

Vulnerable Populations

This study will not include special populations. The criteria for the intended population will exclude groups designated as special populations.

Setting

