Fifty women who are postmenopausal, have moderate or severe entry dyspareunia and meet Friedrich's criteria for vestibulodynia will be recruited into the study. We are assuming a baseline pain score of 70 ± 21.5 (mean \pm std) from a previously reported study of a mixed group of treated and untreated postmenopausal patients with dyspareunia, (Kao, 2012), and we assume a 30% treatment effect after four weeks with the lower-dose intervention drug. A sample size of 50, divided into two arms, allowing for a 10% drop out rate in each of two arms, will achieve >85% power to detect at least 20 points mean difference in dyspareunia pain scoring between the two intervention drug strengths at 4 weeks, with an alpha level of 0.05 for two-sample t-test.

The tissue biopsy sub-group will be 10 subjects from each intervention arm (n=20), and using a one-sided exact test with alpha level of 0.05, this number of subjects will achieve 80% power to detect a difference of 15.6% in inflammation, assuming the baseline proportion of moderate or strong inflammation is 95%. (Leclair, 2013). Patients' biopsies at 3 months will be compared to their baseline biopsy.

To establish a reference group of biopsy specimens, we wish to seek out 5 subjects to fulfill the exploratory aim of assessing the histologic profile of vestibule tissues in postmenopausal women who are not on estrogen and do not have penetrative pain. The prevalence of this type of patient has not been established. We would expect them to have atrophy but no vestibular inflammation or neural hyperplasia. They will not technically be "controls" for purposes of this study. As there are no published studies analyzing the histologic character of the vestibule in such women, the small exploratory number (n=5) does not allow a power analysis. We will recruit these subjects with the help of our Urogynecology colleagues who are doing a study on the vaginal/bladder microbiome and are screening postmenopausal patients.

Swabs with material for microbiome analysis will be analyzed with the help of the Urogyn bioinformatics specialist using QIIME bioinformatics software.

13. Privacy, Confidentiality, and Data Security

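### Primary endpoint 4 concerns the speed and uniformity of pain correction, but the only pain analysis described compares mean scores between strengths at week 4

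*Combined protocol and SAP*

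**What the plan says.** Section 2 lists four primary endpoints. The fourth is dyspareunia on the NRS during nightly therapy, "determining how soon and how uniformly this schedule corrects painful penetration in study subjects". Hypothesis 3a in the same section predicts correction of moderate or severe dyspareunia in more than 62% of women. Primary goal 2 is to compare the efficacy of the two strengths.

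Section 12 is the only analysis section. For pain it gives a sample-size statement: a "baseline pain score of 70 ± 21.5" is assumed, then "we assume a 30% treatment effect after four weeks with the lower-dose intervention drug". With 50 women and 10% dropout per arm, the stated aim, at more than 85% power, is to "detect at least 20 points mean difference in dyspareunia pain scoring between the two intervention drug strengths at 4 weeks". The method named is a t-test for two samples at the 0.05 level. The rest of the section covers an exact test for biopsy inflammation, the comparison of 3-month with baseline biopsies, the reference group, and microbiome software. It describes no time-to-correction, responder, repeated-measures or variability analysis of pain, and does not define correction.

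On data collection, inclusion criterion 9 asks for willingness to use the "Tampon Test as many as 2 times per week" and to attempt intercourse if that test shows penetration to be tolerable. Under Section 9, diaries record pain from either a Tampon Test or a sexual encounter. They are collected or reviewed at weeks 4, 8 and 12. VPAQ questionnaires are completed at Visits 1, 4 and 6.

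**The concern.** The endpoint asks two things of the nightly schedule: how quickly it works and how consistently it works across women. The first needs data over time, and the second needs the distribution of individual responses. A difference in means between strengths at one visit supplies neither. Both arms also use the same nightly schedule, so a contrast between strengths says nothing about how fast that schedule works.

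If only the described analysis were run, the trial would report one mean difference at week 4. It would give no estimate of onset, spread or proportion corrected, and no test of hypothesis 3a. The analyses needed would then be chosen after the data are in hand, with the definition of correction, the time window and the type of penetration all open. On a listed primary endpoint, that invites selective reporting.

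**Working it through.** **1. The plan's own figure.** Section 12 gives N = 50, two arms (1:1 assumed), 10% dropout, a 20-point difference, SD 21.5 and alpha 0.05 (two-sided assumed).
- Evaluable per arm: 25 × 0.9 = 22.5.
- Standardised difference: 20/21.5 = 0.930.
- Noncentrality: 0.930 × √(22.5/2) = 3.12.
- Power from the noncentral t: 86.2%, or 85.4% at 22 per arm.

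The stated figure of more than 85% reproduces, so the arithmetic is sound for the week-4 question.

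**2. Uniformity cannot be read from a mean.** A 30% fall from 70 gives a mean of 49. Take two illustrative week-4 distributions, each with mean 49 and SD 21.5.
- Normal: share at or below 20 points = Φ((20 − 49)/21.5) = 8.9%.
- Mixture: 25% of women centred on 15, and 75% on (49 − 0.25 × 15)/0.75 = 60.33. The common SD is √(462.25 − 0.25 × 34² − 0.75 × 11.33²) = 8.77. Share at or below 20 = 0.25 × Φ(5/8.77) + 0.75 × Φ(−40.33/8.77) = 17.9%.

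The proportion with low pain doubles while the mean and SD stay the same. The 20-point cut is only for illustration.

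**3. Data with no described use.** Weeks 5-12 are 8/12 = 67% of treatment. At the ceiling of two Tampon Tests a week, that is up to 16 of 24 scores per woman. The real number will be lower, because the criterion sets a maximum and not a schedule.

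**4. The 62% benchmark.** Assume 45 evaluable women (50 × 0.9) and an exact one-sided test at 0.05. The smallest r with P(X ≥ r | 0.62) ≤ 0.05 is 34 of 45 (75.6%). Its actual level is 0.040; r = 33 would give 0.077.

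| True rate | Power |
|---|---|
| 70% | 26% |
| 75% | 55% |
| 80% | 83% |
| 85% | 97% |

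**5. Timing between arms.** If 62% of 45 women are corrected, there are about 28 events. Log-rank power is Φ(√28 × ln(HR)/2 − 1.96). This gives 19%, 45%, 68% and 83% at assumed hazard ratios of 1.5, 2, 2.5 and 3. A comparison of timing between strengths could only be descriptive, while a pooled description of onset remains feasible.

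**The case against.** The t-test has a legitimate job. It addresses primary goal 2 directly and is adequately powered on its own assumptions. In a self-described pilot, onset and uniformity may reasonably be descriptive. Both points stand. They argue for keeping the week-4 contrast and against demanding power for the rest, but a descriptive summary of a primary endpoint still has to be stated.

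Two stronger readings are tempting, and the documents support neither.

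- **A reader might infer that the plan uses one diary value per woman and discards the rest.** The t-test appears only inside the sample-size statement. Nothing says whether the 4-week score is one diary entry, an average, or a questionnaire item. Later scores are not excluded; no use for them is described. Counting unused scores would also overstate the loss, because repeated scores overlap in information. At an assumed within-woman correlation of 0.5 to 0.8, 24 scores carry as much as 24/(1 + 23ρ), or 1.9 to 1.2, independent ones.
- **A reader might infer that averaging diary scores would clearly raise power.** That needs the full 20-point difference to hold throughout the averaging window and 21.5 to be a single-score SD. Suppose instead that the difference builds linearly to 20 points at day 28. Four scores at days 17.5, 21, 24.5 and 28 then average a 16.25-point difference. The SD of the mean is 21.5 × √(ρ + (1 − ρ)/4), which is 17.0 at ρ = 0.5 and 19.8 at ρ = 0.8. At 22 per arm, power is 87% and 76%, against 85% for a single day-28 score. The direction of the change is unknown.

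Pooling the two stimuli would also be unsafe. Whether intercourse is attempted depends on the Tampon Test result, and the Background reports that some women with intercourse pain had no tampon pain. The mix of scores therefore depends on response.

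**Conclusion.** The concern holds as a gap between a primary endpoint and the analysis described for it. The week-4 t-test is valid for comparing strengths, with power of about 85-86%, but it cannot show onset or uniformity. Section 12 describes no analysis of weeks 5-12 pain scores and no test of the 62% rate. This follows from the text and needs no assumption. The documents do not show that the planned test is wrong, that data will be thrown away, or that a given amount of power is being lost. Any power gain depends on the within-woman correlation and on how the effect builds up, and neither is given. The calculations for timing and for the 62% benchmark assume 45 evaluable women, with hazard ratios and true rates chosen for illustration. The change should be made, though it does not undermine the sample size.

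**What to change.** Amend Section 12 before unblinding.

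1. **Week-4 contrast.** Keep it as the powered comparison. Estimate it from a mixed model for repeated NRS scores with strength, week, strength-by-week and baseline pain, and report the week-12 contrast beside it. State the NRS range and which diary days count as each week.
2. **Baseline.** Name its source. Diaries are first dispensed with study drug and no pre-treatment diary period is described, so the Visit 1 questionnaire is one candidate, provided it has an item on a comparable scale.
3. **Stimulus.** Analyse Tampon Test and intercourse scores separately, with one named in advance as the main measure. Do not combine them in a 14-day mean.
4. **Definitions.** Define correction and sustained correction on the NRS.
5. **How soon.** Give Kaplan-Meier curves of time to correction, pooled and by arm, labelled descriptive.
6. **How uniformly.** Give the proportion corrected at weeks 4, 8 and 12 with exact intervals, and compare one named time point with 62%.

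The cost is plan wording and modest programming, with no new visits, data or participants. The between-arm timing comparison will have low power, and the 62% comparison is well powered only if the true rate is about 80% or more.

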The standard regimen for local estrogen supplementation was approved by the FDA for the primary outcome of vaginal atrophy (Suckling 2006). The regimen that lowers pH and converts an immature maturation index to a mature index is the following: two weeks of daily intravaginal estrogen by any of several low-dose products such as cream or tablets. Once the atrophy is corrected, the maintenance regimen doses the same estrogen product twice weekly. The vaginal mucosa responds quite quickly to this dosing schedule of estrogen. After 2005 the FDA began requiring that products correct more than atrophy. They required that products also assess "the most bothersome symptom" (Ettinger, 2008). These symptoms could include irritation, itching or a sense of dryness and perhaps dyspareunia. No studies to date have assessed the effect of estrogen on pain at the vestibule, which is the likely site of tenderness, nor what dosing regimen is required to address pain instead of atrophy.

Urinary symptoms are part of the Genitourinary Syndrome of Menopause. For this reason, we are collaborating with our urogynecology colleagues to explore some bladder issues that our cohorts may exhibit. Evolving research has pointed to the role that microorganisms play, and hormone status has a strong relationship to urinary tract health. It has become possible to evaluate microbial communities with techniques that are culture-independent using a DNA-based approach (Brubaker, 2015). From locally collected swabs from the vestibule and vagina we will characterize the resident microbial community using a DNA-based approach by amplifying the bacterial 16S ribosomal RNA (rRNA) gene via PCR. We will perform next-generation sequencing using Illumina MiSeq (Metzker 2010). This will be analyzed with the help of the urogynecology biostatistician using QIIME bioinformatics software.

Because dyspareunia is a pain condition whose provocation is vaginal intercourse, it has been important to have a proxy maneuver that does not involve a sexual partner. Foster and colleagues tested and validated the Tampon Test using a hygiene item with which most women have had experience (Foster, 2009). It was validated in pre-menopausal women with dyspareunia and Goetsch used it in her postmenopause study (Goetsch, 2015). Not all subjects had tampon pain despite all having intercourse pain. It is the only proxy test accepted by experts in vulvar pain.

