Subjects who do not speak English will not be enrolled.

9. Procedures Involved

This study includes up to 7 visits as outlined below:

Visit 1 (Screening Visit)

- Consent
- Review of inclusion/exclusion criteria
- Medical/surgical and medication history
- Pelvic examination to assess genital atrophy and vestibule tenderness

- Vestibule tenderness assessment will include the cotton-swab touch test (a test of mucosal sensitivity) and the lidocaine test (application of 4% aqueous lidocaine to tender mucosa for 3 minutes with reassessment of the cotton swab test to assess by what percentage the mucosal pain has been extinguished).
- The initial cotton swab used to map the tenderness in the vestibule and one from a vaginal side wall sample will be labeled, frozen and stored for later batched analysis of the microbiome composition.
- Transvaginal ultrasound to assess endometrial stripe thickness
 - Since subjects will have been selected because of having pain with vaginal penetration, it will be assumed that the vaginal probe used for the ultrasound examination will not be comfortable for the subject to insert without some preventative treatment. The study clinician will pre-treat the location of tenderness with 4% aqueous lidocaine for several minutes prior to insertion of the vaginal probe. This should prevent or minimize local pain from the vaginal probe.
- Blood sample collection for serum β-estradiol
- Completion of questionnaires
 - Demographics
 - Vulvar Pain Assessment Questionnaire (VPAQ), modified, #1
 - Lower Urinary Tract Symptoms (LUTS) questionnaire
- Randomization to study drug by Research Pharmacy, after all eligibility criteria confirmed by study staff
- Vulvar biopsy (for those subjects enrolling in the sub-study)
 - If participant agrees to biopsy, the baseline sample can be collected at either V1 or V2, dependent on subject preference
 - 4mm vestibule punch biopsy at the 4 or 8 o'clock site next to one of the Bartholin duct orifices after the zone has been pretreated with topical 5% lidocaine ointment for 10 minutes

Visit 2 (Enrollment/Randomization) - ***THIS VISIT MAY BE COMBINED WITH VISIT 1***

- Confirmation of inclusion/exclusion criteria
- Update to medical and medication history
- Dispensing of study drug with review of how to use/apply by study staff
- Dispensing of diary forms and review of instructions for documentation
- Dispensing of Tampons

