 - O Diary questions include pain scoring of either a Tampon Test (a validated test used to assess vestibular tenderness), or a sexual penetration encounter

Visit 3 (12 hour blood draw +/- 60 minutes)

• Blood sample collection for serum β-estradiol [12 hours after the initial study drug dose (8 or 9am after an initial dosing at 8 or 9pm the evening before)]

Visit 4 (week 4 +/- 3 days)

- Update to medical and medication history
- Review of possible symptoms associated with study drug
- Collection and review of diary, additional pages dispensed as needed
- Pelvic examination to assess genital atrophy and vestibule tenderness
- Blood sample collection for serum β-estradiol
- Completion of questionnaire, VPAQ #2

Visit 5 (week 8 +/- 3 days) – telephone or email contact only

- Update to medical and medication history
- Review of possible symptoms associated with study drug
- Review of diary

Visit 6 (week 12 +/- 3 days)

- Update to medical and medication history
- Review of possible symptoms associated with study drug
- Collection and review of diary
- Pelvic examination to assess genital atrophy and vestibule tenderness
- Collection of swabs from the vestibule and from the vaginal side walls for later analysis of the microbiome composition.
- Repeat transvaginal ultrasound to assess endometrial stripe thickness
- Blood sample collection for serum β-estradiol
- Completion of questionnaires: VPAQ #3 and LUTS questionnaire
- Remaining study medication collected from participant by study staff
- Repeat vulvar biopsy (for those subjects enrolled in the sub-study)

Visit 7 (follow-up)

• Subjects will be contacted by phone, mail or email 4 months after study completion to ask the status of their dyspareunia and estrogen regimens and to administer follow-up questionnaires (VPAQ modified + LUTS questionnaire).

Long-term follow up

Study staff may request permission to contact subjects by telephone or email for up to 5 years to ask the status of their pain and any medication they are using to treat their pain.

Duration of Participation:

The duration of active participation will be 12 weeks and limited further data will be obtained from a phone call, mail, or electronic communication 7 months after enrollment into the study. Participants may be asked to allow additional follow-up contact for up to 5 years after their last study visit.

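### Diary pain is described only for attempts made, with no minimum test schedule, so the proportion corrected would be overstated if women in more pain skip attempts

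*Combined protocol and SAP*

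**What the plan says.** Section 2 (Primary endpoints, item 4) measures dyspareunia on the NRS with the aim of "determining how soon and how uniformly this schedule corrects painful penetration in study subjects".

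The between-visit pain record is the diary. Section 9 (Visit 2) describes it thus: "Diary questions include pain scoring of either a Tampon Test (a validated test used to assess vestibular tenderness), or a sexual penetration encounter". How often a score should arise is indicated only in section 5, inclusion criterion 9: "Willingness to evaluate the progress of therapies by use of the Tampon Test as many as 2 times per week", together with "willingness to attempt intercourse if the Tampon Test indicates tolerable penetrative pain". No minimum number of tests, no set days and no definition of tolerable pain are given. Inclusion criterion 6 admits women who "may have stopped having intercourse due to this consistent experience of pain".

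Section 12 specifies a two-sample t-test between strengths at 4 weeks. It gives no window for the week-4 score, no rule for weeks without a score, and no analysis of time to correction or of uniformity.

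**The concern.** Every diary score that the plan describes needs an attempt at penetration. A woman whose pain is still severe may leave a week blank and remain within the plan. A woman who is improving may record tampon scores and, later, intercourse scores as well. Whether a score exists can therefore depend on the quantity being measured.

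If so, the scored weeks are a favourable selection: pain levels read too low and the share of women corrected reads too high. That matters for primary endpoint 4 and for any responder rate set beside the 62% benchmark in hypothesis 3a. It also matters because the reason for a blank week cannot be recovered reliably once the diary has been collected.

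**Working it through.** **1. The plan's own figure.** Section 12: 50 women in two arms, 10% dropout, SD 21.5, difference 20 points, alpha 0.05. Taking 1:1 allocation and a two-sided test (neither is stated), 25 × 0.9 = 22.5, so 22 to 23 women per arm. The noncentral-t power is 0.854 with 22 and 0.870 with 23. The stated power above 85% is reproduced, provided all of these women have a week-4 score.

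**2. Inputs for the illustration.**
- Lower-strength mean at week 4: 70 × (1 − 0.30) = 49 (section 12).
- Higher-strength mean: 49 − 20 = 29 (the detectable difference in section 12, taken in favour of the higher strength).
- SD 21.5 in each arm (section 12), on a 0–100 scale.
- Assumed, because the documents give no value: a cutoff *c* below which a woman counts as corrected; 90% of women below *c* record a score; a share *r* of those at or above *c* do.

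**3. True and observed correction.**

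True pooled proportion: p = ½[Φ((c − 49)/21.5) + Φ((c − 29)/21.5)].

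Observed proportion among women with a score: 0.9p / [0.9p + r(1 − p)].

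For c = 40: p = ½(0.338 + 0.696) = 0.517. With r = 0.5, observed = 0.465 / (0.465 + 0.242) = 0.658.

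| Cutoff | True | Observed, r = 0.5 |
|---|---|---|
| 20 | 21% | 33% |
| 30 | 35% | 50% |
| 40 | 52% | 66% |
| 50 | 68% | 79% |

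Varying r at a cutoff of 40 gives 58% (r = 0.7), 62% (r = 0.6), 66% (r = 0.5) and 76% (r = 0.3). The observed value exceeds p whenever r is below 0.9. The upward direction therefore follows from avoidance itself and not from the choice of cutoff; the size depends on both.

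**4. How much missingness this implies.** At c = 40 and r = 0.5, the share scoring is 0.9 × 0.338 + 0.5 × 0.662 = 64% in the lower-strength arm and 0.9 × 0.696 + 0.5 × 0.304 = 78% in the other. About 29% of all women have no week-4 score.

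**5. Other summaries (same model, scores clipped to 0–100, r = 0.5).**
- *Levels:* at c = 40 the arm means fall from 49.0 and 29.9 to 44.2 and 26.2. Both are too low.
- *Difference between strengths:* true 49.0 − 29.9 = 19.1. Observed 44.2 − 26.2 = 18.0 at c = 40, but 46.5 − 25.3 = 21.2 at c = 20. It can shrink or widen.
- *Spread at c = 40:* the SD goes from 21.1 to 21.5 in the lower-strength arm and from 19.9 to 18.3 in the other. There is no single direction.

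**6. Adding intercourse scores.** A second illustration lets intercourse follow half of tolerable tampon tests. Its assumptions are: tolerable is 40 or less; within-woman SD 10; log-odds of a tampon attempt 1.5 at pain 30, falling by 2 per 50 points.
- If tampon and intercourse hurt equally, the lower-strength week-4 diary mean is 43.7 against a true 49.0. The fall from baseline is 61.0 − 43.7 = 17.3 against a true 69.2 − 49.0 = 20.2, so the level flatters while the improvement is understated.
- If the tampon is 20 points milder, adding intercourse scores raises the diary mean from 26.5 to 34.2, which works against apparent correction.

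**The case against.** The strongest reply is that the Tampon Test was chosen because it needs no partner. Every treated woman agrees to it, tampons are handed out at Visit 2, and staff collect and review the diary at week 4. High-pain weeks can therefore be scored. Criterion 9 states willingness; it does not bar earlier intercourse. Criterion 6 concerns giving up intercourse, not the tampon. All of this stands: pain-related skipping is plausible but not documented, and the illustration's 29% without a score is heavy.

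The diary form itself is not among the documents. Visit 2 lists "Dispensing of diary forms and review of instructions for documentation", and the description of the diary questions is not exhaustive, so a response for attempts not made may already exist. Nor do the documents say outright that the NRS endpoint, or the week-4 t-test, uses diary scores. That is inferred, because no other listed procedure could show timing between visits.

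The modified VPAQ and the pelvic examination for tenderness take place at Visit 1, week 4 and week 12 whether or not a diary attempt was made. They mitigate the problem, but they serve secondary endpoints and cannot show when correction occurred between visits.

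A reader might infer three stronger things that the documents do not support:
- *The 62% benchmark would be crossed falsely.* With r = 0.5, only the cutoff of 40 among the four moves the result across 62%. No cutoff is given in the plan, and hypothesis 3a is not set at week 4.
- *The trial as a whole is biased towards correction.* Section 3 reports of the investigators' previous study that "Not all subjects had tampon pain despite all having intercourse pain", so adding intercourse can raise scores, and measured change can be understated.
- *Women will look more uniform than they are.* The spread does not narrow consistently.

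**Conclusion.** The concern holds in a limited form. As written, the plan lets the existence of a diary score depend on the pain that primary endpoint 4 is meant to track, and it states no minimum schedule and no rule for weeks without a score. If women in more pain skip attempts, pain levels are understated and the proportion corrected is overstated, by about 11 to 15 percentage points across cutoffs of 20 to 50 under the assumed 90%/50% scoring. At a cutoff of 40 the overstatement is about 6 points if 70% of women in pain still score and about 24 if only 30% do. These sizes rest on assumed scoring rates, assumed cutoffs and the week-4 means implied by section 12. No direction should be claimed for change from baseline, for the difference between strengths or for uniformity. The point should be dealt with because the remedy is cheap and the missing information cannot be recovered later.

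**What to change.** In the Visit 2 diary instructions, and to match in inclusion criterion 9:

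- Set the Tampon Test on two fixed days each week for all 12 weeks, continued after intercourse resumes.
- Add two diary responses: *not attempted because of pain* and *not attempted, other reason*.

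In section 12:

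- Say whether the NRS endpoint is taken from the diary, and take the week-4 score from a fixed window, for example days 22–28.
- Count pain-related non-attempts as not corrected.
- Add a sensitivity analysis of the week-4 comparison in which pain-related non-attempts are ranked as the worst outcome.

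The cost is diary wording and a short amendment. The testing load stays within the twice-weekly limit that women already accept. Women who would have skipped tests carry slightly more burden, and the reported correction rate may be less favourable.
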